Secondary Outcomes / Covariates				
Social Determinants of Health				
Environmental and social factors	X			
Gout medical care				
Number of gout flares (Gaffo criteria) ^{79, 84}	X	X	X	
Rates of urate lowering therapy (ULT)**	X	X	X	
ULT adherence		X	X	
Opioid prescriptions*	X	X	X	
Weight reduction		X	X	
Healthcare resource utilization (visit number)				
ED visits (indicative of recidivism)*		X	X	
Hospitalizations*		X	X	
Health-related quality of life				
European Quality of Life (EQ-5D) ⁸⁶⁻⁸⁸	X	X	X	
Shared decision making: CollaboRATE scale ⁹⁰		X	X	

* gout follow-up within 3-months of ED visit. ** Assessed through chart or system review

randomized 2:1 stratified by race/ethnicity, to the intervention (storytelling +/- patient navigation) or control arm (usual care). All intervention arm patients in the UAB ED also will be assigned lay navigators to provide personalized support for care transitions and access to post-gout flare medical services needed for preventing recurrent flares.

The following procedures will be completed during the index ED visit:

- Review inclusion/exclusion criteria for registry participation
- Informed Consent
- Review of current/past gout status and medication chart review
- Pain Assessment
- Laboratory
 - Serum uric acid (from chart review)
 - Sample banking
- Survey assessments
 - HRQL
 - SDOH

Laboratory draw will be done in conjunction with ED care blood draw when possible. At the conclusion of visit, participants randomized to navigator arm will be provided navigators picture, contact information, and informed that they will receive a call w/in 72 hours.

B.9.1.2 *Patient Navigator Contact*

72 hours post ED visit

During this initial phone conversation the navigators will: 1) conduct a baseline assessment to identify barriers to attending an outpatient visit for gout care (e.g. transportation) and to adhering to gout treatment recommendations (medications, diet, exercise) and, 2) determine the level of support and assistance (e.g. transportation support) needed by patient. The patient navigator will help facilitate the follow-up visit with a primary care/gout specialist, identify any barriers (e.g. lack of trust in primary care physician or/and healthcare system), and provide institutional/community resources that can be mobilized for the patient.

4 weeks post ED visit and 24-48 hours prior to appointment (anticipated)

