The navigator will conduct two additional follow-up calls at approximately one month (4 weeks) and in the week (anticipated) prior to their visit to confirm the appointment time, the level of support needed (as needs may have changed), and encourage him/her to keep their appointment. In the unlikely event that the appointment with the PCP/gout specialist is sooner than one month, this one-month pre-appointment call will be eliminated and the navigator will have only two calls with the patient.

B.9.1.3 *6 Week Follow-up Assessment*

At 6 weeks following ED visit, participants will be contacted by the Coordinating Center (CC) to to assess project outcomes via a telephone survey. The following information will be collected, and data collected via the surveys and EMR. Following completion of the follow-up surveys the study coordinator will inform and debrief the patient that they participated in a study evaluating methods to improve continuity of gout care. The debrief will be conducted after the 1st survey. If RA the coordinator is unable to reach participant on the phone, the survey questions used to collect the primary outcomes will be sent via email or text messaging using Mosio, which is an HIPAA-compliant application.

- Survey assessments
 - Patient satisfaction
 - HRQL
 - PROs
- Updated medical history and review of concomitant medications
- Assessment of Adverse Events (AEs) (as meeting NIH definition of Phase III study AEs will be collected)

B.9.1.4 *3 Month Follow-up Assessment*

At 3 months (anticipated) post ED visit participants will be contacted to complete a second follow-up survey and end of study (EOS) via telephone to assess secondary outcomes (e.g. adherence to orders, medication RX, and labs (if ordered)).

- Survey assessments
 - Patient satisfaction
 - HRQL
 - PROs
- Updated medical history and review of concomitant medications
- Assessment of Adverse Events (AEs) (as meeting NIH definition of Phase III study AEs will be collected)

B.9.1.5 **Table 1 Visit Schedule**

Visit description / Study procedures	Screening and Enrollment (ED)	V1 (phone)	V2 (phone)	V3	V4 EOS
	Day 0	72 Hours	4 WK	6 WK [°]	3 MO
Review of Inclusion/exclusion criteria following alert notification	X				
Informed consent for INSIGHT Registry	X				
Medical history	X				
Laboratory					
SUA	X				
Sample banking	X				
Randomization	X				
Patient Navigator Contact#		X	X ^{\$}	X ^{\$}	
Updated medical history and concomitant medications		X	X	X	X

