Outcome ascertainment	X			X	X
Study debriefing				X	
Assess AEs			X	X	X

[°]Primary outcome assessment will occur at any point upto 6 weeks post ED visit dependent on routine care visit; # For individuals randomized to navigation arm; ^{\$}Navigator will contact participant in the week prior to scheduled follow-up visit

B.9.1.6 **Blinding and Unblinding**

Participants will blinded to study assignment at enrollment, and following primary outcome ascertainment will be debriefed regarding the study and its purpose/goals.

B.10 Statistical Analysis Plan

B.10.1 Primary Outcome Analysis - Aim 1.

All analyses will adhere to the principles of rigor, reproducibility and transparency.^{109, 110} To determine the effectiveness of our alert system, we will examine the diagnostic properties (sensitivity/specificity) of the EMR alerts against a gold standard of NLP/ML detection (section C.4.2)

B.10.2 Primary Outcome Analysis- Aim 2.

Descriptive statistics, including measures of central tendency (means for continuous, proportions for categorical) and dispersion (variance, interquartile range) will summarize the distribution of baseline characteristics of randomized patients seen in both EDs. Descriptive statistics will be summarized by treatment arm as well as enrollment site. These statistics will inform the successfulness of randomization in creating comparable groups and ascertain our success in recruiting the populations we seek to target (particularly under-represented minorities). We also will compare the descriptive characteristics between those participants who do and don't respond to follow-up surveys to detect and report any evidence of a selective non-response bias. The primary analysis approach for testing treatment effect will be a multivariable logistic regression

model. We have chosen multivariable logistic regression over Cochran-Mantel-Haenszel approaches to allow for effect estimation of multiple covariates (race, gender, age) upon the primary outcome and to allow tests of interactions. Logistic regression models, including interaction terms, will be developed for 6 week outcomes and 3 month outcomes. We will examine the significance of the effects of the intervention as the outcome of persons receiving at least one outpatient gout follow-up visit at 3 months. We will analyze rates on an intent-to-treat basis for the primary analysis. We will conduct all analyses using SAS 9.4 (Cary, NC)

[figure not shown]

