As this study meets the NIH definition of a clinical trial, and as outlined in our data safety monitor plan we will collect information including diagnosis errors and participant anxiety from answering questions about their health status. All AEs will be captured on the appropriate electronic case report form.

An **Adverse Event (AE)** is defined as any untoward medical occurrence in a participant who received study intervention regardless of its relationship to the study intervention. This determination will be made by the study

principal investigator. Preexisting conditions will not be considered adverse events; however, worsening of a preexisting condition may be considered an AE. AEs will be assessed as to their relationship to the research, severity, and duration. They will be documented appropriately, regardless of the relationship, with start dates occurring any time after informed consent until 7 days after the last day of study participation. AEs will be reported in aggregate to the Safety Officer (SO), Institutional Review Board (IRB) and NIAMS (through the Executive Secretary) as part of the routine safety report.

A Serious Adverse Events (SAE) is any AE that results in death, is life-threatening, results in or prolongs hospitalization, or causes a permanent, persistent or significant disability. SAEs will be reported to the SO, IRB, and NIAMS (Executive Secretary) within 48 hours of the investigator becoming aware of the event. All SAEs will be followed until satisfactory resolution or until the site investigator deems the event to be chronic or the participant is stable.

An Unanticipated Problem (UP) includes any incident, experience, or outcome that is unexpected and possibly related to participation in the research. UPs will be reported to the SO, IRB and NIAMS (Executive Secretary) within 48 hours of the investigator becoming aware of the event.

A protocol deviation is defined as any substantial divergence from the IRB-approved study protocol. Any protocol deviation impacting patient safety will be reported to the SO, IRB and NIAMS (Executive Secretary) within 48 hours of the investigator becoming aware of the event; all other deviations will be reported as a part of the routine safety report.

For additional details see Data Safety Monitoring Plan.

D. Study Sites

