Investigational study sites are the University of Alabama at Birmingham and Vanderbilt University Medical center, two large academic medical centers. The study site staff will ensure participants are consented and randomized in accordance with established good clinical research practices. Additionally, site investigators and their staff will be required to have prerequisite human subjects training, and will answer study related questions, as needed.

- University of Alabama at Birmingham (UAB), Birmingham, AL, United States
- Massachusetts General Hospital (MGH), Boston, MA, United States
- MetroHealth Medical Center, Cleveland, OH, United States
- University of Iowa, Iowa City, IA, United States

Approximately n= 168 participants will be enrolled at the UAB site and n = 112 from MGH, MetroHealth, and University of Iowa study sites.

D.1 Participant Recruitment and Consent

The site study staff will:

- Provide participants with adequate information concerning the study procedures, and scope
- Provide adequate opportunity for the participant to consider all available options
- Respond to the participant's questions and concerns
- Ensure that each participant understands all information provided
- Obtain the participant's written voluntary consent to participate
- Sign the consent form as witnesses
- Provide participants with a copy of the consent form

D.2 Participant Retention/Discontinuation

Participants will have the option to withdraw from the study at any time. Study staff will make at least 3 attempts to contact participants for study intervention visits (ie, Patient Navigation at UAB, MGH, MetroHealth,

and University of Iowa) and outcomes assessment surveys at 6 weeks and 3 months. In order to minimize the chances of losing touch with patients, study staff are collecting email addresses and secondary contact names and phone numbers at the original emergency department visit.

If study staff are not able to reach participants after at least 3 phone attempts, they will attempt to reach the secondary contact listed and/or send an email or text message to the participant. Text messages will be sent through the Mosio application, which is an HIPAA-compliant application. If these methods are not successful in contacting participant, then participant will be considered lost to follow up.

D.3 Site Monitoring

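### The adverse event definition turns on receiving the study intervention, and the schedule adds AE and medication reviews at times when only navigator calls are described, so control-arm events may go unrecorded and a by-arm AE summary would be uneven

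*Combined protocol and SAP*

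**What the plan says.** **Definition (section C).** An AE is "any untoward medical occurrence in a participant who received study intervention regardless of its relationship to the study intervention". The section does not define the intervention. An SAE is a subset of AEs (death, life threat, hospitalization, disability) and must be reported within 48 hours. AEs count if they start after informed consent, up to 7 days after the last day of participation, and go to the Safety Officer, IRB and NIAMS in aggregate.

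**Use of the term elsewhere (D.2).** Staff make at least three attempts to reach "participants for study intervention visits (ie, Patient Navigation at UAB, MGH, MetroHealth" and Iowa), and for the 6-week and 3-month surveys. No other kind of contact is named.

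**Visit schedule (B.9.1.5).** The row "Updated medical history and concomitant medications" is marked at 72 hours, 4 weeks, 6 weeks and 3 months. The AE row is marked at 4 weeks, 6 weeks and 3 months. The navigator row is marked at 72 hours, 4 weeks and 6 weeks, with the footnote "For individuals randomized to navigation arm".

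**Navigator calls (B.9.1.2).** At 72 hours the navigator is to "conduct a baseline assessment to identify barriers to attending an outpatient visit for gout care" and settle the support needed. Then: "The navigator will conduct two additional follow-up calls at approximately one month (4 weeks) and in the week (anticipated) prior to their visit". If the appointment falls within a month, "this one-month pre-appointment call will be eliminated and the navigator will have only two calls with the patient". Neither AE nor medication review is listed as a navigator task.

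**Common assessments (B.9.1.3, B.9.1.4).** Both the 6-week and the 3-month assessment include "Assessment of Adverse Events (AEs) (as meeting NIH definition of Phase III study AEs will be collected"), with no limit to one arm.

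**The concern.** There are two separate problems.

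The first is who can have an AE at all. If the study intervention means navigation, or the intervention arm's package, then a death or hospitalization in a control participant is not an AE. It is therefore not an SAE and does not trigger 48-hour reporting. The harms that section C singles out, diagnosis errors and anxiety from health questions, can arise equally in controls, who go through the same alert, interview and surveys.

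The second is who is asked, and how often. If the 72-hour and 4-week reviews happen only on navigator calls, the navigation group has one more occasion to report an AE and a shorter recall period for early events. A by-arm AE table built from all contacts would show an excess that has nothing to do with harm. Nothing in the protocol says how events first heard on navigator calls are to be handled.

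**Working it through.** **1. Does the AE definition fit the rest of the plan?** Set side by side:
- Definition: participants who received the study intervention.
- Window: opens at informed consent, before anyone has received anything.
- Reviews at 6 weeks and 3 months: participants without limit to an arm.
- D.2: uses the term for navigation. B.9.1.1 describes the control arm as usual care.

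A literal reading leaves the window and the common reviews collecting control-arm events that the definition does not recognise. The same reading would drop an intervention-arm participant whom the navigator never reached.

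**2. Contacts per arm, from B.9.1.5.** This assumes that the 72-hour and 4-week contacts are navigator calls only.

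| | 72 h | 4 wk | 6 wk | 3 mo | Navigation | Control |
|---|---|---|---|---|---|---|
| AE assessment | no | yes | yes | yes | 3 | 2 |
| Medication review | yes | yes | yes | yes | 4 | 2 |
| Outcome ascertainment | no | no | yes | yes | 2 | 2 |

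Outcome ascertainment is also marked at the ED visit, in both arms. The AE difference is a single call. It vanishes for anyone whose appointment falls within a month, which B.9.1.2 regards as unlikely; B.5.3 cites average waits of 9 to 10 weeks for a rheumatologist.

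**3. Size if all contacts were pooled.** The plan has no figure to reproduce and no detection rate. Assume equal true risk and a chance q that an event is reported at each contact after it occurs. For an event before the 4-week call:

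apparent risk ratio = [1 − (1 − q)³] / [1 − (1 − q)²]

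- q = 0.5: 0.875 / 0.750 = 1.17
- q = 0.7: 0.973 / 0.910 = 1.07
- q = 0.9: 0.999 / 0.990 = 1.01

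For the concomitant medication record (4 versus 2 contacts), [1 − (1 − q)⁴] / [1 − (1 − q)²] gives 0.9375/0.750 = 1.25, 0.9919/0.910 = 1.09 and 0.9999/0.990 = 1.01.

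**4. A second model, over the whole follow-up.** Assume events spread evenly over 13 weeks, so a fraction f = 4/13 falls before the 4-week call. Assume 90% capture at that call, 80% capture of later events, and a 6-week recall r of early events:

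ratio = [f(1 − 0.1(1 − r)) + 0.8(1 − f)] / [f r + 0.8(1 − f)]

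- r = 0.6: 0.849 / 0.738 = 1.15
- r = 0.8: 0.855 / 0.800 = 1.07

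**5. Sensitivity to site.** B.9.1.1 assigns navigators to intervention patients at UAB; D.2 names navigation at all four sites. Section D plans 168 participants at UAB and 112 elsewhere, so UAB is 168/280 = 60%. If navigation is at UAB only, with the same allocation and event rate at every site, the arm-level excess is 0.6 times the figure above. The range 1.01 to 1.17 becomes about 1.005 to 1.10, and 1.07 to 1.15 becomes about 1.04 to 1.09.

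**The case against.** **No AE comparison is planned.** B.10 contains none, and section C reports in aggregate. This stands. A reader might infer that the trial's arm comparison of AEs is already biased; the documents do not support that. The bias arises only if someone tabulates AEs by arm from all contacts.

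**The trial's medication outcomes are safe.** A reader might infer that urate-lowering therapy and opioid outcomes are better captured in the navigation arm. They are not taken from the extra calls. Table 2 schedules both at the ED visit, week 6 and month 3, marks urate-lowering therapy rates as chart or system review, and the outcome row of the schedule is blank at 72 hours and 4 weeks. This stands in full.

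**The arm restriction is inferred.** The footnote sits on the navigator row alone. The AE and medication rows carry no restriction, and navigators are given no AE task. This partly stands: the plan never says that controls get no early call. But B.5.3 describes none, D.2 lists only navigation visits and the two surveys, and no other early call appears anywhere. If navigators do not do the reviews, the 4-week AE assessment has nobody assigned to it in either arm, which also needs repair.

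**The definition can be read broadly.** Controls receive attention-control material on the tablet, which might count as an intervention, and a Data Safety Monitoring Plan outside these documents may be clearer. Unanticipated problems are also defined without reference to receiving the intervention. So it goes too far to say that control events are certainly excluded. But a control-arm hospitalization unrelated to the research would not be an unanticipated problem, and a safety definition should not depend on a charitable reading.

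**Conclusion.** The concern holds in two limited parts. First, the AE definition conflicts with the plan's own collection window and common reviews, and on its literal reading leaves control-arm AEs and SAEs outside the reporting rules. This is the more important part and rests on no assumption beyond the wording. Second, the schedule supports, without stating, one extra AE contact and two extra medication reviews for participants who get navigation. Any by-arm AE summary that pooled all contacts would be tilted against navigation, with an apparent risk ratio of roughly 1.01 to 1.17. The detection rates are assumed, the early contacts are taken to be navigator-only, and the upper end applies to events before the 4-week call with poor detection at each contact. Navigation at UAB alone would shrink the excess. The primary outcome and the scheduled secondary outcomes are not touched.

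**What to change.** - **Section C:** define AEs and SAEs for every consented participant in either arm, whatever was received.
- **Any by-arm AE summary:** use only the 6-week and 3-month assessments, and have each ask about the whole interval since the previous common contact (the ED visit, then week 6).
- **Navigator-call events:** record the source on the AE form, list these events separately, and still report them for safety on the usual timelines.
- **Schedule:** reconcile B.9.1.5 with B.9.1.1, B.9.1.2 and D.2 on who performs the 72-hour and 4-week reviews, in which arm and at which sites.

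The cost is wording and one source field on the AE form. No calls are added and the sample size is unchanged. A by-arm summary would contain slightly fewer events, because those reported only to a navigator move to the separate listing.

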Our e-Consent platform includes components designed through the STRIDE project to enhance the informed consent process in a health literacy and culturally sensitive manner, utilizing a simplistic layout with essential features of the consent process described at launch, socio-demographically diverse avatars (selected by patients) that walk through elements of the consent process, definitions for complex terms, and videos to demonstrate procedures. Storytellers share their experiences in research in a way that touches upon key elements, e.g. why research is important, societal gains from research participation and what to expect throughout study participation. The process of IC will be carried out by one of the study investigators in conjunction with the ED study coordinator/research assistants (RA) involved in the screening visit after the participant appears to meet the inclusion criteria above. ED RAs will invite patients in both study arms to enroll in the Gout Registry and Biorepository and will utilize enhanced informed consent material. During the initial ED visit, the RA will provide the study participant the electronic consent tool and launch the REDCap application. In keeping with the guidelines established by the revision of the Common Rule (Federal Register Volume 82, No. 12), the informed consent form (ICF) will begin with and include a summary with key information on the “5 factors” about the study that will be provided to facilitate the subjects’ understanding of the proposed research and also ensure that they understand how their data and bio-specimens may be used. This includes a statement that 1) the project is research and participation is voluntary; 2) a summary of the research that will outline duration, purpose, and responsibilities of all parties involved; 3) potential risk or discomforts with participating; 4) potential benefits; and 5) alternatives to participation. In addition, the consent will outline the collection and the use of any private information and how specimens collected for laboratory analysis will be used. Patients will provide electronic informed consent before any study procedures are performed. In addition, we will utilize enhanced consent materials developed for STRIDE to enhance minority participation. To enhance participation in our gout registry we will modify the STRIDE REDCap-based e-Consent platform specifically for the GOUT registry and deploy culturally-sensitive stories with actual patients who have previously participated in registry-based research, which will describe the experience of participating in clinical registries.

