
Participants will be given as much time as they need to read and ask questions about the ICF. The individual or patient’s legally authorized representative will be informed that he/she is not obligated to participate in the study and that it is strictly voluntary and that he/she may withdraw from the study at any time and that withdrawal of consent will not affect his/her subsequent medical treatment or relationship with the treating physician. The IC process will ensure that there is no penalty for not participating in a clinical trial and that treatment will not be compromised if individuals do not participate, or if they cease participation at any time.

By signing the electronic consent form, the participant authorizes the use of their personal health information (PHI), that they understand the study and its benefits and risks, and agree to all other aspects of the study outlined in the form. It allows the participant the opportunity to decide whether they want to participate in a study. During this process, individuals will be informed of all aspects of the study so that they can make an informed decision. Participants will then confirm their willingness to participate in the research study by signing the ICF. A signed version of the consent form will be kept by the study staff in REDCap database and emailed to the participant following consent.

The ICF contains the following:

- Disclosure of relevant information to prospective participants about the research
- The participant's comprehension of the information
- The participant's voluntary agreement to participate in a research study without coercion or undue influence
- Complete disclosure of any appropriate alternative procedures and their risks and benefits
- Disclosure of the extent of confidentiality that will be maintained
- Statement of compensation and/or medical treatment available if injury occurs
- Name, address, and telephone number of the PIs

If there is a change in any of the study procedures that may affect the participant, the ICF will be revised and approved by the Institutional Review Board (IRB). Any participants enrolled in the study prior to a change in procedures will sign the amended consent form. Signed consent forms will be kept as part of the study record for at least 7 years after completion of the study. Participants can withdraw their consent at any time by informing the study coordinator.

B.7 Data Management and Entry

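### Participant blinding (B.9.1.6) cannot be maintained as written: B.6 discloses the study beforehand, navigator patients are told of calls in the ED, and the debrief precedes the 3-month outcome

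*Combined protocol and SAP*

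**What the plan says.** On blinding, B.9.1.6 reads: "Participants will blinded to study assignment at enrollment, and following primary outcome ascertainment will be debriefed regarding the study and its purpose/goals".

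On disclosure, B.6 says: "Patients will provide electronic informed consent before any study procedures are performed". The consent summary it describes includes the purpose of the research, and it adds that "individuals will be informed of all aspects of the study so that they can make an informed decision".

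On what patients learn in the ED, B.9.1.1 says that "participants randomized to navigator arm will be provided navigators picture, contact information, and informed that they will receive a call w/in 72 hours". B.5.3 gives controls an attention control: tablet material on preventive health that does not concern gout.

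On the debrief, B.9.1.3 has the coordinator "inform and debrief the patient that they participated in a study evaluating methods to improve continuity of gout care", and adds: "The debrief will be conducted after the 1st survey". That first survey is at 6 weeks, and the visit schedule (B.9.1.5) marks the debriefing in the same column.

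On the outcome, B.8.1 defines the Aim 2 primary outcome as the proportion with a follow-up visit addressing gout within 3 months of the ED visit. Self-report is the primary source, with EMR review alongside. B.8.1 accepts recall and social desirability bias on the ground that it should be non-differential.

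On consent in the schedule, the one consent row in B.9.1.5 is "Informed consent for INSIGHT Registry". B.6 says: "ED RAs will invite patients in both study arms to enroll in the Gout Registry and Biorepository".

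**The concern.** A participant who has been told the purpose and every aspect of a study cannot later be debriefed on that purpose as news. Either B.6 is not followed or the debrief has little left to reveal. The protocol therefore claims participant blinding that its own procedures do not deliver.

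This matters because the primary outcome is the patient's own report of a visit, and one arm is telephoned and encouraged to make and keep that visit. If participants know or guess what is wanted of them, over-reporting can differ by arm. It would then push the estimate away from the null, opposite to the direction B.8.1 relies on. A trial report that described participants as blinded would give readers unwarranted reassurance on this.

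The consent row is a smaller, separate matter. A schedule that shows randomisation but only registry consent leaves the order and independence of the two consents unclear.

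**Working it through.** **1. The passages side by side**

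| Question | One account | Other account |
|---|---|---|
| Is the purpose known at entry? | Yes: consent precedes any procedure and covers purpose and all aspects (B.6) | No: purpose explained at a later debrief (B.9.1.3, B.9.1.6) |
| Is assignment hidden? | Yes, at enrolment (B.9.1.6), with an attention control (B.5.3) | Navigator patients get a picture, contact details and notice of a call (B.9.1.1), then the calls (B.9.1.2) |
| Does the debrief follow the primary outcome? | Yes (B.9.1.6) | No: it follows the 6-week survey, and the outcome runs to 3 months (B.9.1.3, B.8.1) |

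On the third row, a footnote to the visit schedule puts primary outcome assessment at up to 6 weeks, and B.9.1.4 describes the 3-month survey as assessing secondary outcomes. Only on that reading is the debrief on time. B.8.1, B.10.2 and B.11 all use 3 months, and Table 2 lists the primary outcome at both times. Taking 3 months as about 13 weeks, the debrief leaves about 13 − 6 = 7 weeks of the window still open.

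**2. How many patients are told of navigator calls**

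Inputs: 168 participants at UAB and 112 at the other sites, 280 in all (section D); 2:1 allocation; every UAB intervention patient has a navigator (B.9.1.1).

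- Intervention arm: 280 × 2/3 ≈ 187. Controls: 280 − 187 = 93.
- UAB intervention patients: 168 × 2/3 = 112.

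So at least 112 of about 187 intervention patients are told, and none of about 93 controls. D.2 mentions patient navigation at all four sites, in which case the figure could be all 187.

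**3. The plan's own power figure**

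Inputs from B.11: 200 patients at 2:1 (67 control, 133 intervention), control rate p₀ = 0.30, relative risk 1.68, two-sided α = 0.05. So p₁ = 0.30 × 1.68 = 0.504.

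Power = Φ[(|p₁ − p₀| − 1.96 × SE₀) / SE₁], with SE₀ from the pooled rate and SE₁ unpooled.

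- Pooled rate = (67 × 0.30 + 133 × 0.504)/200 = 0.4357; SE₀ = 0.0743; SE₁ = 0.0708.
- Power = Φ[(0.204 − 1.96 × 0.0743)/0.0708] = 79.5%, against the stated 80%. The figure reproduces.

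**4. What differential self-report could do (illustration)**

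Assumptions that are not in the documents: true attendance is 30% in both arms, controls do not over-report, and a share f of intervention non-attenders reports a visit. The reported intervention rate is 0.30 + 0.70 × f. The same formula then gives the chance of a significant result in favour of the intervention.

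| f | Reported rates | Apparent RR | Chance of false benefit |
|---|---|---|---|
| 0% | 30% v 30% | 1.00 | 2.5% |
| 5% | 30% v 33.5% | 1.12 | 7.0% |
| 10% | 30% v 37% | 1.23 | 15.9% |

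For f = 5%: SE₀ = 0.0701, SE₁ = 0.0693, and Φ[(0.035 − 1.96 × 0.0701)/0.0693] = 7.0%. The documents give no value for f. The table shows only that modest differential reporting would matter, and in which direction.

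**5. Consent structure**

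For a registry gate on trial entry: the single consent row in B.9.1.5, and the B.9.1.1 checklist line that reviews criteria for registry participation. Against: B.6 describes consent to the research study, the same B.9.1.1 checklist has a general informed consent line, the eligibility criteria in B.2 contain no registry or biobank condition, A.2 names the interventional study and the registry as two things, and B.6 words the registry as an invitation. The weight lies with two separate consents and a schedule that labels only one.

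**The case against.** The strongest reply is that B.9.1.6 claims little: blinding to assignment at enrolment. Controls also get tablet material. A patient told to expect a call knows what they will receive, but recognises it as an assignment only if they also know what the other arm gets. That depends on the consent text, which is not in the review copy. This stands, and it limits the conclusion. A reader might infer that the blinding does not exist at all. The documents do not support that, because a consent form that withheld the hypothesis, together with the attention control, could keep some masking until the debrief. But such a form would contradict B.6, and the debrief would still come before the 3-month window closes.

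It is also fair that EMR capture gives a partial check on self-report, although B.8.1 concedes that it misses care outside the participating systems.

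A reader might further infer that refusing the biobank bars a patient from randomisation, or that registry uptake under Aim 3 cannot be measured. Neither is supported. No passage makes registry consent a condition of entry. The wording about patients in both arms says who is invited, not that allocation came first. B.8 defines no registry-uptake endpoint, and uptake could be counted among patients approached, whom B.3 reports monthly.

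Lastly, a reader might infer that disclosure costs power by prompting controls to attend. Both arms would read the same consent. At 196 responders, if both rates rise by 5 or 10 points, power is about 78% or 77%, against 79% with no rise. If the relative risk of 1.68 is kept at control rates of 35% or 40%, power is 89% or 96%. A serious loss needs a rise confined to controls, for which the documents give no basis.

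**Conclusion.** The point holds in this form. The blinding statement is incompatible with the B.6 consent wording, is weakened in the ED for at least 112 of about 187 intervention patients, and lapses at 6 weeks under a 3-month primary outcome. Participant blinding cannot be maintained as written, and the claim that self-report bias is non-differential is left without support.

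The conflict rests on the protocol text alone. The count rests on the section D site totals and exact 2:1 allocation. The size of any bias is unknown: the 7% to 16% range follows from assumed over-reporting of 5% to 10% in one arm only. What patients were actually shown at consent cannot be judged from these documents. The registry row is a defect of the schedule, not evidence of a biobank gate.

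**What to change.** 1. Restate B.9.1.6: participants are not blinded to what they receive. Say what, if anything, about the hypothesis or the outcome is withheld and until when, subject to IRB approval.
2. Align B.6 with that statement, so that disclosure of all aspects and a later debrief no longer coexist.
3. Do not report the trial as participant-blinded.
4. Move the debrief to after the 3-month survey, and reconcile the 6-week footnote in B.9.1.5 with B.8.1.
5. In the schedule, list trial consent before randomisation and a separate, optional registry and biorepository consent. State that declining the registry does not bar randomisation.
6. Report EMR-confirmed visits as a sensitivity analysis for the primary outcome, noting the outside care they miss, and remove the reliance on non-differential self-report.

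The cost is one IRB amendment to the protocol and eConsent text, and the loss of the participant-blinded label. Anything withheld would stay withheld for about 7 weeks longer, which the IRB must accept. The EMR data are already planned for collection, so item 6 adds only analysis.
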